6.2 Fidelity

While this study will look backwards onto how the Mosie Kit was used and resulting pregnancy rates, it also affords the opportunity to examine variations in timing of the insemination with respect to ovulation as well as the frequency of insemination within a cycle. The study will not influence how the Mosei Kit was used, but it is hoped that the information gathered will add understanding to whether timing and frequency might have played a role in pregnancy results. It is important to study how people use Mosie because timing and dosage might impact the pregnancy rate. It is also important to understand the variations in use.

6.2.1 Interventionist Training and Tracking

No intervention will be performed.

6.3 Measures to Minimize Bias: Randomization and Blinding

This study will not have any masking or randomization. It is a retrospective study. Participant selection bias will be minimized by including all people who have purchased a Mosie Kit in the prior 2-8 whole months.

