5.5 Strategies for Recruitment and Retention

Recruitment of participants will be conducted via a direct email campaign. Participants will receive multiple emails requesting their participation in the study. Specifically they will receive emails according to the following schedule:

	Email Content	Expected Date
Initial Email	Initial Invitation to participate	Day 0
Second Email	Reminder of invitation to participate	Day 7
Third Email	Reminder of invitation to participate	Day14
Fourth Email	Last week to participate survey	Day 21
Fifth Email	Final email - 2 days left to complete survey	Day 28

If the study duration is expanded, a weekly email and a reminder a couple of days prior to the new deadline will be sent.

Typical response rates vary between 5-30% for email surveys. The rate of response is higher when people have a connection with the company or product. They also go up with repeated reminders and incentives to participate. A good survey response rate is about 50%.

Participants who complete the survey will receive a code to purchase a future Mosie Kit at a discount. This discount code will also be a code used in other marketing efforts in order to help reduce the likelihood a participant's status of participating in the study will remain masked.

The expected response rate for this study is between 30-50%. This response rate is expected because the potential participants will have all previously purchased a Mosie Kit. Additionally, the Mosie Newsletter has about a 20% open rate so it is expected that participation might be slightly higher than this.

Because participants will only be selected from people who have previously purchased a Mosie Kit there will be a limit in the mix of people available for selection for study participation. This means the results might not be generalizable to the public in general, nonetheless it is a representative sample of the people who would do at-home insemination.

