9.2 Sample Size Determination

The desired final sample size for this study is 500 completed surveys. This will produce a 95% confidence interval with +/- 4.4% within larger populations. In order to obtain that rate of respondents, the study will invite about 50% people who have ordered a Mosie Kit in the prior 2-8 months to the study start date. It is expected that approximately 4000 people will be invited to participate. By inviting 4000 potential participants, it is expected that with a response rate of 15% approximately 600 will complete the survey. Currently Mosie has about a 20% open rate on their general emails. For this reason, all people who purchased a kit within the last 2-8 months will be invited to participate.

According to the sample size tables, a response rate of 384 is sufficient to provide a 95% confidence interval with a 5% margin of error rate. While the total number of respondents can not be controlled, every effort will be made via the reminder emails to obtain at least 500 participants but no less than 384.

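### Inviting every purchaser does not control self-selection among those who answer, and no planned analysis shows how far it could move the primary pregnancy rate

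*Combined protocol and SAP*

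**What the plan says.** Section 6.3, on measures to minimise bias, notes that there is no masking or randomisation and gives one measure against selection bias: "Participant selection bias will be minimized by including all people who have purchased a Mosie Kit in the prior 2-8 whole months". Section 5.5 concedes that results may not extend to the general public, then adds that "it is a representative sample of the people who would do at-home insemination". Section 4.1 describes the sample as one of convenience.

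The two statements of expected response differ. Section 9.2 plans about 4000 invitations and says "with a response rate of 15% approximately 600 will complete the survey". Section 5.5 says "The expected response rate for this study is between 30-50" percent.

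On precision, section 9.2 says "The desired final sample size for this study is 500 completed surveys" and "This will produce a 95% confidence interval with +/- 4.4% within larger populations". It gives the fallback as "a response rate of 384 is sufficient to provide a 95% confidence interval with a 5% margin of error rate". No other uncertainty is attached to the primary rate.

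Section 9.1 tests Primary Hypothesis 1 by setting the overall pregnancy rate among respondents against an external IUI figure of 10-20%. There is no concurrent control.

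**The concern.** Two selection steps lie between the purchasers and the analysed sample: who is asked and who answers. Section 6.3 deals with the first and presents that as minimising selection bias. The second is left to the invitee, and whether the person conceived could plausibly affect the decision to reply.

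Nothing in sections 9.1 to 9.4 addresses this. All the analyses, including the subgroup and exploratory ones, use respondents only. No weighting, bounds, early-versus-late comparison or sensitivity analysis is planned. Other design choices close off the usual checks: incomplete surveys are discarded (7.2), the mailing list is withheld from the investigator (10.1.3), and no outside records are joined to the survey data (10.1.9.1). Reminders and the discount code may raise response, but they do not measure bias.

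Because the comparator is a fixed number, response bias has no counterpart in a control group against which it could cancel. More completed surveys narrow the sampling margin and leave this error untouched.

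**Working it through.** **Inputs from the documents.** 4000 invited; 15% response (9.2) or 30-50% (5.5); target 500 and minimum 384 completed surveys with margins of 4.4 and 5 points (9.2); benchmark 10-20% (9.1).

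**Input assumed.** r, the probability that a conceiver responds divided by the probability that a non-conceiver responds. The documents give no value, so a range on both sides of 1 is used.

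**Step 1: reproduce the plan's figures.** The margin is 1.96 × √(0.25/n).
- n = 500: 4.38 points (stated 4.4).
- n = 384: 5.00 points (stated 5).
- Completers: 4000 × 0.15 = 600.

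All three agree. The formula is for simple random sampling with a proportion of 0.5 and has no term for non-response. At rates of 15-20% the sampling margin for n = 500 would be smaller still, 3.1 to 3.5 points.

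**Step 2: non-response.** It is 85% under section 9.2 and 50-70% under section 5.5.

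**Step 3: rate among respondents.** With true rate p, observed rate = p·r / (p·r + 1 − p). For p = 0.20 and r = 2 this is 0.40 / (0.40 + 0.80) = 33.3%.

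| r | true 10% | true 15% | true 20% |
|---|---|---|---|
| 0.5 | 5.3% (−4.7) | 8.1% (−6.9) | 11.1% (−8.9) |
| 1.25 | 12.2% (+2.2) | 18.1% (+3.1) | 23.8% (+3.8) |
| 1.5 | 14.3% (+4.3) | 20.9% (+5.9) | 27.3% (+7.3) |
| 2 | 18.2% (+8.2) | 26.1% (+11.1) | 33.3% (+13.3) |

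Bias in points is in brackets. At a true 20%, the biases for r = 0.5, 1.25, 1.5 and 2 are 2.0, 0.9, 1.7 and 3.0 times the 4.4-point margin.

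**Step 4: ratio at which bias equals the margin.** r = (p + b)(1 − p) / [p(1 − p − b)]. With p = 0.20 and b = 0.044: 0.244 × 0.80 / (0.20 × 0.756) = 1.29. For three margins (b = 0.132): 0.332 × 0.80 / (0.20 × 0.668) = 1.99.

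**Step 5: dependence on the response rate.** The overall response rate does not appear in the formula. At p = 0.20, r = 2 means 25% against 12.5% responding when overall response is 15%, 50% against 25% when it is 30%, and 83% against 42% when it is 50%. All three are feasible.

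**Step 6: tipping ratios for an observed 25%.** This is the odds of the observed rate divided by the odds of the benchmark.
- Against 20%: 0.25 × 0.80 / (0.20 × 0.75) = 1.33.
- Against 15%: 0.25 × 0.85 / (0.15 × 0.75) = 1.89.
- Against 10%: 0.25 × 0.90 / (0.10 × 0.75) = 3.0.

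**Step 7: effect on a test, as illustration.** The plan names no test for Primary Hypothesis 1. Take an exact one-sided 0.05 test against 20% with n = 500, which rejects at 116 or more pregnancies (23.2%). With a true 15%, the chance of rejecting is about 0 at r = 1, 12% at r = 1.5 and 94% at r = 2. With a true 20% it is 4% at r = 1 and 98% at r = 1.5. In the other direction, a true 30% at r = 0.5 reads as 0.15 / (0.15 + 0.70) = 17.6%, below the rejection threshold.

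**The case against.** **The statement in 6.3 is partly right.** Inviting the full list does remove selection by the investigator, and sections 4.1 and 5.5 disclose a convenience sample and limited generalisability. This stands, so the claim in 6.3 is overstated rather than wholly wrong. The concession in 5.5, however, contrasts purchasers with the public, not responders with non-responders. Section 9.2 also speaks of inviting about half of purchasers before saying that all will be invited, and this should be settled because 6.3 relies on the full list.

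**The 85% figure is not settled.** A reader might infer from 9.2 that 85% of users will be missing. Section 5.5 implies 50-70%. Never-users are excluded (5.2) and screened out (5.4), so non-response among eligible users is lower than among invitees by an unknown amount. This stands, but for a given r the bias is the same at any of these rates.

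**The direction is unknown.** A reader might infer that the rate will be inflated because happy users reply. The documents do not support that. The incentive in the invitation emails is a discount on a future purchase, and two of the five subject lines in Appendix C feature it. That could draw people still trying to conceive. This stands, and is why r must be examined below 1 as well as above it.

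**The size is assumption-driven.** At r = 1.25 the bias is below the 4.4-point margin for true rates of 10-20%. Quoting only the 1.33 tipping ratio would also pick the least favourable end of the benchmark. Both points stand.

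**Conclusion.** The concern holds in a limited form. Inviting all purchasers does not minimise self-selection, the quoted margins describe sampling error only, and no planned analysis would show how sensitive Primary Hypothesis 1 is to differential response.

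The size depends wholly on r, which is an assumption. At a true rate of 20%, the error reaches the stated margin at r = 1.29 and three times the margin at r = 2. At r = 0.5 it is about twice the margin in the opposite direction. The documents do not show that the rate will be too high, that the error will be several times the margin, or that 85% of eligible users will fail to respond.

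The study can run as designed. An unqualified conclusion that the kit is equivalent to or better than IUI would not be supported.

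**What to change.** 1. **Wording.** In 6.3 and 5.5, remove the claims that selection bias is minimised and that the sample is representative. In 9.2, state that the 4.4% and 5% margins cover sampling error only. Reconcile the 15% and 30-50% response rates.
2. **Tipping-point table.** Pre-specify for Primary Hypothesis 1 a table of the response ratio at which the conclusion would change, with r on both sides of 1 and benchmarks across 10-20%. Showing the whole range matters because the plan does not fix a single benchmark value. Report an equivalent-or-better conclusion only alongside that ratio.
3. **Optional wave check.** Use a separate generic link in each of the five emails and report the pregnancy rate by email wave. This keeps the survey anonymous. It is indicative only: a link shows which email was clicked, and late responders are merely a proxy for people who never respond.

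The cost is edits to three sections, one extra table that needs no new data and, if item 3 is adopted, five links in place of one. The downside is a less strongly stated headline conclusion.

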6.4 Study Intervention/Experimental Manipulation Adherence

This study does not have an intervention. However data will be collected on the self-administered intervention that will be examined retrospectively. The data will allow determination as to whether the minimum intervention was followed, i.e. administration of two

at-home insemination instances one within 24 hours of initial signs of ovulation and one at 24-48 hours after confirmed ovulation.

6.5 Concomitant Therapy

N/A

6.5.1 Rescue Therapy

N/A

STUDY INTERVENTION/EXPERIMENTAL MANIPULATION DISCONTINUATION AND PARTICIPANT DISCONTINUATION/WITHDRAWAL

7.1 Discontinuation of Study Intervention/Experimental Manipulation

N/A

7.2 Participant Discontinuation/Withdrawal from the Study

Participants may choose to leave the survey at any time without submitting the completed survey. There will be no way to know which participant did not complete the survey or why the survey was not completed. There will be no way to follow up with the participant to request continued participation as the survey will not contain any identifying information.

There will be no replacement participants. Any incomplete surveys will be discarded automatically by the system. They will not be available for use in the final analysis.

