2.3 Risk/Benefit Assessment

2.3.1 Known Potential Risks

Since this is a retrospective study and the participants will have already used the Mosie Kit, there is no potential additional physical risk from participating in the study. In some cases, because fertility is a sensitive issue, some people might become a bit emotional in recalling unsuccessful attempts to get pregnant. Otherwise, there are no known additional risks for participating in this study.

This retrospective study will be conducted as an anonymous one-time self-report survey that will contain no personal information that will allow the participant to be identified. This is done to

reduce the risk of the information being associated with the individual providing the information. This also ensures there are no immediate or long-term risks associated with participation.

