10.1.1.2 Consent Procedures and Documentation

After reading the consent form, the participant can elect to proceed to the survey or conclude the survey. The only documentation collected about the consent is whether or not the participant elected to respond to the questions. A consent is not required for participation in this study. Answering the questions and submitting the responses provides consent. Only completed surveys that are submitted will end up in the database.

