10.1.9.1 Data Collection and Management Responsibilities

Google forms will be used to collect this one time survey. The only data quality checks that will be included in the survey will be those that are implemented via the appropriate selection of the type of field in order to ensure the appropriate data is entered into the field and edit checks to ensure all questions are filled in.

The online Google Form and resulting excel sheet will constitute the source data for this study. No external records or information will be combined with the survey data. Only the PI and the Sponsor will have access to download the data.

Data standards will be implemented for the study. Descriptive field names will be used for each field. All data collection is the responsibility of the PI. The PI is responsible for ensuring the accuracy and completeness of the data.

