Appendix A: Online Survey Tool and Consent Form (Google Form)

This section shows what the Google Form will look like to the study participant. These are the questions the participant will be asked.

The first page of the study contains the consent form and the question that confirms the participant's agreement to participate.

There is skip logic for certain sections. For example, if the participant selects one cycle of using Mosie, the information related to cycles 2-6 will be skipped. If the participant selects that she is pregnant the questions related to the pregnancy will be asked, otherwise they will be skipped. If a donor was used, the questions related to producing a sperm sample will be skipped.

Note: Final language and questions might be tweaked or revised at any time to increase clarity.

MOSIE-001 © 2020 Mosie Baby Page 38

[figure not shown]
This is the inclusion/exclusion form.

If Participant selected to not participate in the study, he/she will see this screen next. If the participant said he/she is not 18 or older or has not used Mosie this screen will be displayed.

[figure not shown]

Qualifying participants will continue the survey on this page.

[figure not shown]

[figure not shown]
	ch of these diagnoses or issues do you believe are contributing to your rtility? *
	Not applicable
	PCOS
	Endometriosis
	Low AMH or low ovarian reserve
	Low Sperm count
	Sperm motility issues
	Erectile Dysfunction
	Performance issues or sexual anxiety, or inability to orgasm with partner
	Vaginismus or vulvodynia
	Tilted Uterus
	Multiple uterus/cervix
	Unexplained infertility
	Have only one functioning fallopian tube
П	Other:

[figure not shown]
No other method	is attempted			
Male/Female into	ercourse			
IVI or syringe oth	ner than Mosie			
IUI				
Femara				
Clomid				
IVF				
Cervical Cap				
Other:				
	None	1	2	3 or more
How many pregnancies have you had?	0	0	0	0
pregnancies	0	0	0	0
pregnancies have you had? How many live births have you had? How many pregnancies have you had that were	0	0	0	0
pregnancies have you had? How many live births have you had? How many pregnancies have you had	0	0	0	0

[figure not shown]

[figure not shown]
	0	1	2	3+
24-48 hours prior to ovulation	0	0	0	0
within 24 hours of ovulation	0	0	0	0
24-48 hours after ovulation	0	0	0	0
48+ hours after ovulation	0	0	0	0
Did you use Mosie fo Yes No	or another cy	cle?		

[figure not shown]

[figure not shown]

[figure not shown]

[figure not shown]

Mosie Kit Survey

* Required

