[figure not shown]
How did you or your partner time your ovulation? (Select all that apply.) *
Count days in cycle
Track vaginal or cervical fluids
Tracking changes in the cervix
Use ovulation predictor kit
Use an app to estimate ovulation
Basal Body Temperature
Wearable device
Did not time ovulation
Did using Mosie result in a pregnancy? *
O Yes
O No
Back Next Page 10 of 20

[figure not shown]
Never submit passwords through Google Forms.

 $This \ content \ is \ neither \ created \ nor \ endorsed \ by \ Google. \ \underline{Report \ Abuse} - \underline{Terms \ of \ Service} - \underline{Privacy \ Policy}$

Google Forms

Page 56

[figure not shown]

Safe process

Enjoyable

	Very Easy	Easy	Neutral	Difficult	Very Difficult
To collect the semen/sperm sample in the cup?	0	0	0	0	0
To draw up the semen/sperm in the syringe?	0	0	0	0	0
Insert the Mosie syringe into the vagina up to the handles?	0	0	0	0	0
To deposit the semen/sperm at or near the cervix using the syringe?	0	0	0	0	0
My overall impression on the ease of use	0	0	0	0	0
					Page 12 of 20
submit passwords to	through Google Fo				

MOSIE-001 © 2020 Mosie Baby Page 59

MOSIE-001 © 2020 Mosie Baby

Page 60

Pulled the syringe plunger back and forth to confirm it was functioning.

My partner washed their hands

Use a sperm friendly-lubricant.

Thawed out donor sperm from sperm bank

Prepared all items and have them handy ready to use.

Washed the penis

that	apply)?*
	Lie down in a comfortable position.
	Relax
	Receive oral sex
	Stimulate clitoris
	Use any vibratory or non-vibratory stimulation device intravaginally
	Have an orgasm
	Other:
	erall, how well were you able to use the Mosie syringe to inseminate yourself our partner? * Very Able
	our partner? *
or y O O O	our partner? * Very Able Able Not Very Able
or y 0 0 0 0	Very Able Able Not Very Able Not Able at All Volume at All Volume at All Volume at All Volume at All Able at All Volume at All Able at All Able at All
or y O O O	Very Able Able Not Very Able Not Able at All Volong did you remain laying down after using the Mosie syringe? * Less than 15 minutes

Willelf best descri	ibes your lying position? *	
On my stomach	n	
On my side		
On my back		
On my back wit	th my hips elevated by a pillow	
Other:		
O No		
O		
What type of sam	ple did you use? *	
What type of sam	ople did you use? * rom a sperm bank (frozen)	
What type of sam	rom a sperm bank (frozen)	

0 2000	thank 50%	
O 51%-	70%	
O 71% -	80%	
O 81%-	90%	
O 90%-	95%	
O 96%-	100%	

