Multiracial o	r Multiethnic	
Black or Afri	can American	
Hispanic or	_atinx	
· White		
Native Amer	ican or Alaska Native	
Native Hawa	iian or other Pacific Islander	
Asian Ameri	can	
Indian Amer	can	
Other		
What is your ap	proximate household income?*	
Choose	•	

Hov	v would you describe yourself? *
0	Woman
0	Man
0	Transgender
0	Non-binary
0	Prefer not to say
0	Other:
0	Single/Not in a relationship LGBTQ Relationship Other:
Are	you married? *
0	Yes

	ID 17 directed you	ır family building	plans? *	
O Yes				
O No				
If yes, pl	ease share how it h	as affected you	r family building	g plans.
Your ansv	ver			
Is there	anything else you w	ould like to sha	re with us?	
Your answ	ver			
	Next			Page 1
Back				, and the second
	asswords through Googl			

Mosie Kit Survey

THANK YOU! We so appreciate you!

Use code WARMHUGS for 15% off your next purchase.

If you did conceive with the Mosie Kit, we'd love to celebrate your joyful news and send you a special baby gift. Email us at [contact] to share your news!

If you're still on your journey to conceive, we are sending you big hugs! We want to help and support you as best we can, no matter the path taken, we are here for you! If you have any questions or if you're interested in sharing your current journey to conceive with the Mosie Community, email us at [contact]. Fingers crossed for you!

Our thanks and best wishes to you! Team Mosie Baby

This content is neither created nor endorsed by Google. Report Abuse - Terms of Service - Privacy Policy

Google Forms

MOSIE-001 © 2020 Mosie Baby Page 79

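### A user who reports her pregnancy result on page 10 but does not submit the complete 20-page form drops out of the primary rate unseen; the bias could go either way and its size is unknown.

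*Combined protocol and SAP*

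**What the plan says.** Section 7.2 lets a participant leave at any point and then rules: "Any incomplete surveys will be discarded automatically by the system. They will not be available for use in the final analysis". It adds that neither who left nor why can be known, and that follow-up is impossible. Section 10.1.1.2 agrees: "Only completed surveys that are submitted will end up in the database". Section 10.1.9.1 describes "edit checks to ensure all questions are filled in".

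In Appendix A the primary endpoint is a single required yes/no item, "Did using Mosie result in a pregnancy", and the footer of its page reads "Back Next Page 10 of 20". The later pages cover ease of use (footer page 12), sperm collection (page 14), safety and infections (page 15), the doctor's views (page 16), then demographics and COVID-19. Race and "household income" both carry the required mark. The race options as printed include no refusal choice, although the gender item has one. Income is a drop-down whose options are not visible in the text.

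Section 9 has no count of surveys started, no missing-data method and no sensitivity analysis for lost outcomes. Its only precision figure, in 9.2, is plus or minus 4.4 points at 500 completed surveys.

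**The concern.** These rules act together. The participant may already have given the primary outcome, yet it is kept only if she also gets through every later required item and submits. Some of those items are sensitive and have no bearing on the primary endpoint.

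This is separate from non-response to the invitation. It affects people who took part and reported a result, and it comes from the form and the discard rule, both of which the sponsor controls.

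If the chance of stopping after page 10 is related to whether the user conceived, the observed pregnancy rate is biased. Section 2.3.1 gives one reason why it might be: "some people might become a bit emotional in recalling unsuccessful attempts to get pregnant". Discarded forms leave no trace, so the final data could neither show nor correct the bias.

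**Working it through.** **Inputs from the documents.** Target 500 completed surveys and a margin of 4.4 points (9.2); IUI comparator of 10-20% (9.1, primary hypothesis 1); significance level 0.05, one-tailed for directional hypotheses (9.4.1).

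**Input not in the documents.** Break-off after page 10, by outcome. The values below are assumptions chosen to show the range.

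**Step 1: the plan's own figure.** Half-width = 1.96 × √(0.5 × 0.5 / 500) = 4.38 points, which reproduces the stated 4.4. At a rate of 20% the same formula gives 1.96 × √(0.2 × 0.8 / 500) = 3.5 points. Both are sampling error only.

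**Step 2: shift from discarding.** Let p be the pregnancy rate among people who answer page 10, and let d1 and d0 be the fractions of pregnant and non-pregnant users who then fail to submit.

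Observed rate = p(1 − d1) / [p(1 − d1) + (1 − p)(1 − d0)]

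With p = 20%:

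| Loss, pregnant / not pregnant | Calculation | Observed | Shift (points) |
|---|---|---|---|
| 10% / 10% | 0.18 / (0.18 + 0.72) | 20.0% | 0.0 |
| 2% / 5% | 0.196 / (0.196 + 0.76) | 20.5% | +0.5 |
| 5% / 10% | 0.19 / (0.19 + 0.72) | 20.9% | +0.9 |
| 10% / 5% | 0.18 / (0.18 + 0.76) | 19.1% | −0.9 |
| 5% / 20% | 0.19 / (0.19 + 0.64) | 22.9% | +2.9 |
| 10% / 30% | 0.18 / (0.18 + 0.56) | 24.3% | +4.3 |
| 20% / 5% | 0.16 / (0.16 + 0.76) | 17.4% | −2.6 |
| 30% / 10% | 0.14 / (0.14 + 0.72) | 16.3% | −3.7 |

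For 5% / 10% loss, true rates from 10% to 50% give shifts of 0.5 to 1.4 points.

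**Step 3: what a large shift needs.** A 3-point shift at 20% requires a retention ratio (pregnant to non-pregnant) of (0.23/0.77) / (0.20/0.80) = 1.195. With 5% loss among pregnant users, that means 1 − 0.95/1.195 = 20.5% loss among the others. A 4.4-point shift requires a ratio of 1.291, or 26.4% against 5%.

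**Step 4: effect on a comparison with 20%.** Section 9.1 names no test for primary hypothesis 1, so this is illustrative. An exact one-sided binomial test with n = 500 rejects at 116 or more pregnancies (size 4.3%). If the true rate is exactly 20%, the chance of rejection is 4.3% with equal loss, 11% with 5% / 10% loss and 45% with 5% / 20% loss. It falls to 0.1% with 20% / 5% loss.

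**The case against.** **Direction.** A reader might infer that users who failed over several cycles are lost more often, so that the rate is biased upward. Appendix A says "if the participant selects one cycle of using Mosie, the information related to cycles 2-6 will be skipped", so long users do answer more. But those cycle pages come before page 10. Someone worn out by them leaves before giving an outcome and so cannot lose one already given. The skip also depends on cycles used, not on outcome: a non-pregnant one-cycle user skips the same pages as a first-cycle conceiver. The one branch described as tied to the pregnancy answer adds questions for those who report a pregnancy, which would push the rate down. The reward for submitting, 15% off the next purchase, may also matter more to people still trying. This objection stands: the sign is unknown.

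**Size.** No break-off rate is given, and a shift of several points needs a gap in loss of roughly 15 points. The comparator is a range, not a single cut-off at 20%. Post-page-10 loss is also probably small beside invitation non-response, since 9.2 expects about 600 completions from 4000 invitations. This stands too.

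**How far the items really block.** Some later items carry no required mark or already offer a way out, such as the overall star rating, the home-versus-office item and the not-applicable and did-not-ask-my-doctor choices. The race list has an Other option, and the income list may contain a refusal that the text does not show. This weakens the examples. It does not remove the general rule in 10.1.9.1 or the discard rule in 7.2.

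**Consent.** Inclusion requires submitting the survey, so unsubmitted answers may not be used. That is correct. It limits the remedy to making submission easier, because abandoned answers cannot be recovered.

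**Conclusion.** The defect holds as a loss of primary outcomes through form design, with unknown size and unknown sign. It concerns only people who leave from page 10 onward. It would be tempting to say that anyone who leaves the form loses a known outcome, but people who leave earlier have given none.

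At a true rate of 20%, the shift is nil if loss is equal, about 0.5 to 1 point for a gap in loss of 3 to 5 points, and about 3 to 4 points either way for a gap of 15 to 20 points. All these gaps are assumed. The documents do not support saying that the reported rate will probably be too high, or that a shift of several points is likely. They do show that the plan has no means of detecting such a shift and that the stated 4.4-point margin does not include it. That is enough to justify a cheap design change before the survey opens.

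**What to change.** 1. Keep as required only consent, screening, number of kit cycles, pregnancy result, age, relationship type, fertility issue, and the key safety and ease-of-use items.
2. Make the income, race, sperm-collection, doctor and COVID-19 items optional, or add a choice to decline.
3. Reword 7.2 and 10.1.9.1 so that every submitted survey with the core items enters the primary analysis, and other items are analysed on the answers available. Without this, a submitted form with one blank optional item could still count as incomplete and be discarded.

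The cost is some missing demographic and exploratory answers, a few changed settings in the form, and IRB approval of the amended text. Consent by submission and anonymity are unchanged.

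There are limits. People who close the form without submitting are still lost and still uncounted. Moving the core items earlier stores nothing unless the user can also submit early. An early-submit branch placed before the ease-of-use and safety pages would save some pregnancy results at the expense of the secondary endpoints. That is a trade-off for the sponsor to weigh and is not part of this recommendation.
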